
outcomes from post-trauma limb surgery: perceived social support, self-esteem, coping style and pre-surgical expectations of/post-surgical outcomes. A research technician experienced in psychosocial interviewing with participants will meet with each participant during the baseline evaluation to administer the self-report battery of psychosocial questionnaires. A comprehensive battery of tests for evaluation of quality of life has been assembled for this study. It is important to properly determine the impact of the surgical changes and the investigators have selected psychosocial assessment instruments to evaluate four domains:a. Satisfaction with appearance/surgical outcomes – The Satisfaction with Appearance (SWAP) scale (145) is a 14-item questionnaire with good internal consistency and test-retest reliability that measures both subjective and social-behavioral aspects of body image and has been used in populations with significant physical disfigurements or deformities. b. Satisfaction with Medical/Health Services - Patient Satisfaction with Health Services – the Client Satisfaction Questionnaire (CSQ-8) is a widely used brief inventory of satisfaction with services (amount of help, kind of help, availability of help) provided by a medical service or program (146). c. Social Functioning, Distress, Depression and Avoidance - To evaluate hypothesized pre- versus post-operative changes in quality of life, social functioning, symptomatology and coping, we will include the following measures: • Social Distress and Avoidance - Individuals with disfigurements can suffer extreme anxiety and avoidance in interpersonal interactions. The Social Anxiety and Distress (SAD) Scale (147) is a widely used measure of social avoidance and distress that has shown to be sensitive to pre-/post- surgical improvement in recent studies of patients undergoing reconstructive surgery for significant physical deformity. • Anxiety and Depressive Symptomatology will be monitored using the Beck Depression Inventory, PHQ brief and the PCL-S (Post trauma checklist- Brief) (148), a self-report questionnaire that taps post traumatic stress disorder (PTSD) symptoms for use among individuals in the military. • Self-esteem will be assessed by the Rosenberg Self Esteem Inventory (149), a brief (10-item), a self-report inventory examines how social structural positions relate to self-esteem. • Coping Style will be assessed with the Brief COPE inventory (150) an abbreviated version of the situation-specific coping inventory (151) that has been effectively used to characterize psychological coping with physical illness and disability. An extensive body of research on clinical and psychosocial outcomes from surgical and medical interventions has yielded evidence that psychosocial coping style is an important factor that contributes to psychological well-being, physical health and quality of life outcomes. • Perceived Social Support will be analyzed by the Perceived Social Support Questionnaires(PSSQ)-Family and Friends (152). This 6-item self-report inventory with satisfactory internal reliability and construct validity that inquires regarding the perceived availability of social support for needs for support, information and feedback. Social support, along with psychosocial coping cognitions and behaviors contributes significantly to psychological well-being, physical health and quality of life outcomes. Each of these may be important covariates that contribute to variance in quality of life outcomes in this study.d. Quality of Life and General Functioning Outcomes - Quality of life and general functional status will be evaluated using the SF-36 (153, 154), a self-report inventory

widely used in medical outcome research with self-rated indices of health, quality of life, energy, role limitations due to physical problems or emotional problems, and functionality in everyday physical, emotional, and social function domains.e. A brief (shortened) demographic history form will be completed as part of the psychosocial assessments. This psychosocial evaluation (self-report measure) will take an estimated 1.5-2.0 hours and will take place at the UPMC Plastic Surgery Center in a private room. 8. Pre-Operative Laboratory tests will be obtained via a peripheral blood draw performed by laboratory personnel located on the 5th floor of the UPMC Montefiore Hospital building. Blood tests will not need to be repeated at PGSV if screening blood tests were collected within 30 days of operative procedure date. Blood tests approximately 30mls (2 tablespoons) will be collected for the following laboratory assessments: Serum CBC with Differential and platelets, Comprehensive Chemistry panel, pre-albumin, Albumin and PT/ PTT/ INR. On receiving the pre-op laboratory results, the Investigator will initial and date the results and assign clinical significance to any out of range values. Subjects with clinically significant results attributed to any disease entity will be excluded from the trial. 9. Electrocardiogram (EKG) and or chest x-ray, as indicated by past medical history.10. The study coordinator will provide the participant with a Diary Card and Pain Log with instruction to begin completion of the Diary Card and Pain Log 24 hours after their fat grafting surgery and continue until Post operative Day 3-6. The subject will be instructed to document a self assessment of the following events pertaining to the surgical site: Pain, Bruising, Redness of the skin, Itching, Swelling, Bleeding, Other (any concerns/issues not listed). The subject will be instructed to identify on the Diary Card the location, date and day of each documented event. The subject will be asked to continue completion of logs if an event/issue persists at PO day 3-6 until the next post -op visit (POV1). Per guidance from the FDA, we will plan for a 10-14 day time staggering interval between the administration of the investigational product for each of the first six subjects randomized to the TGI IDE arm of this clinical trial to capture any detrimental or unknown risks associated with the products or procedures, such as anaphylactic reactions to any components of the lipoaspirate or contaminations (during the procedures involving fat harvesting and machine processing of lipoaspirate) which may lead to sepsis. Operative Visit:All surgical procedures will be performed at UPMC Shadyside Hospital located on the 2nd floor, UPMC Magee or Montefiore Hospitals within the operating room suites. These procedures are being conducted as an outpatient admission and all monitoring conducted during the peri-operative care period will be performed per standard practice according to the UPMC policy and procedures for this facility. Prior to the surgical procedure being conducted, the subject will be seen by the research team in the DAS area and at which time PI and co-investigator(s) will mark areas of surgical interest and may document with 2D photographs. Should new areas be identified or included at this time for surgery, photographs will be taken of the areas of interest at this time. The fat graft surgical procedure will be performed at this visit and will take approximately 4-5 hours to complete. The fat grafting is planned as an outpatient procedure which is conducted within the UPMC Shadyside Hospital located on the 2nd floor, UPMC Magee or

Section: Section 2 - Research Design and Methods

Montefiore Hospitals within the operating room suites. In brief, fat tissue to be used for grafting is harvested (usually from abdomen or thighs) with a small liposuction cannula in the operating room. Specific details of the Fat Harvest and Graft Preparation follow: Subjects will receive general anesthesia or a block with sedation. A dilute epinephrine solution (concentration 1:1,000,000) will be injected into the harvest site, which is usually abdominal or thigh subcutaneous tissue. A blunt tip hollow cannula is then used to aspirate through 5mm incisions. Up to 1500cc of lipoaspirate solution mixture will be obtained. This mixture once centrifuged is anticipated to produce an adequate volume of concentrated adipose tissue for injection, cell processing, and research assays. For the 15 subjects randomized to the Autologous Standard fat graft processing we will prepare the fat graft as follows: Once harvested the aspirated fat tissue will be processed as standard graft material. It will be divided into small aliquots and centrifuged in a sterile rotor (3000 rpm for 3 minutes/1200g), and top fluid oil layer from the fat tissue fractions were removed, and transferred into 3mL syringes, each filled with 2.5mL of the lipoaspirate and injected into the amputation stump. This graft preparation will be performed in the operating room. Standard fat graft material will serve as a control treatment and will be injected into limb using specialized injection cannulas as described below ("Fat Graft Placement"). For the 15 subjects randomized to the Autologous Fat Graft enhanced with adipose stromal cell processing we will prepare the cells as follows: Approximately 60-150 cc of lipoaspirate will be collected from the subject to be processed at the HSC lab using the Tissue Genesis Cell Isolation System™ (CIS) to yield approximately 3-8cc of Stromal Vascular Fraction (SVF) suspension. Per the Principal Investigator's clinical evaluation of the area of deficit as it relates to the amount of fat volume necessary to appropriately fill the deficit, the team may employ a second Tissue Genesis Cell Isolation System™ (CIS) concurrently. The aspirated fat processed as standard graft material will be divided into small aliquots and centrifuged in a sterile rotor (3000 rpm for 3 minutes/1200g), and allowed to decant before separating the fluid and oil layers from the fat tissue fractions, and transferred into 60 ml syringes. This graft preparation will be performed in the operating room. a. The lipoaspirate for concentration along with a 5cc aqueous solution syringe for each 60 cc syringe will be transported from the operating room to the Hematopoietic Stem Cell Laboratory (HSC Lab) at the UPMC Hillman Cancer Center, [name]. This facility is directly across the street from the operating room and connected via a connecting bridge. No specimen during transport will be transported outside of a building(s). In brief, this is a state-of-the-art laboratory that was constructed of materials compliant with 21 CFR 211, has a cleanroom that is ISO Class 6, and is GMP compliant with regards to function. This facility is registered with the FDA (FEI# 3004565478), is FACT accredited (since 1999) and is CAP accredited (CAP LAP # 7190853).b. In the Hematopoietic Stem Cell Laboratory (HSC Lab), the stromal vascular fraction (SVF) cell suspension (device output) will be processed using the Tissue Genesis Cell Isolation System™ according to procedures and a cell count will be performed as described in SOP 2008-02-R0. Prior to administration to of the SVF to the subject, rapid endotoxin testing, cell viability, cell count determinations and Gram staining will be

performed as described in SOPs 2005-13-R5 [SOPs are Attached] and 2008-02-R0. The acceptable endpoints are: AO viability \geq 50%; Endotoxin levels $<$ 5EU/kg of recipient ideal body weight, cell yields \geq 1E+05 total SVF cells per mL of adipose stroma and gram stain negative. The determinations will be recorded in triplicate. All handling and procedures with the lipoaspirates and isolation of the SVF are handled in sterile areas and all personnel are appropriately gowned and gloved as well as all laboratory instruments (pipettes, etc.) have been appropriately sterilized/cleaned. c. The released adipose stromal vascular fraction preparation will be transported back to the operating room. The concentrated autologous stromal vascular fraction cells will arrive back in the operating room close to the time that the standard fat graft preparation process is completed. It is anticipated that the time required for preparing the Autologous Stromal cells concentrated fat graft will add no more than 30 minutes to the overall operating time compared to Autologous Standard fat graft processing. d. The Standard graft material and the stromal vascular fraction cells will be mixed and subsequently injected into the amputated stump a target concentration of $2.0 - 3.0 \times 10^6$ stromal vascular cells/ml of injected fat graft is desired in this study. However, we recognize that there will be significant variation in cell yield between patients, as well as variation in required graft volumes. The actual cell dose for each subject will be collected to the intraoperative source document. The procedure for combining the SVF with the lipoaspirate prepared in the operating room will be performed inside the sterile operating room by [name] or a co-investigator who is specifically trained in the techniques of fat graft processing using the [name] method as well as this cell-enrichment technique of combining SVF with lipoaspirate. i. To manually combine the standard fat graft material and the SVF suspension (device output), each of the syringes will be connected via luer to luer lock. The contents of the lipoaspirate syringe are transferred to the SVF syringe and the cell suspension will be injected slowly back and forth between the two (2) syringes. The final 1 mL SVF-fat graft syringe is now considered cell-enriched and ready for injection into the subject. ii. It should be noted that in the event of fat harvest from both abdomen and thigh, abdominal fat grafts will be combined with abdominal fat SVF and thigh fat grafts will be combined with thigh fat SVF. Fat Graft Placement: The plastic surgeon will use the specially designed hollow injection cannulas (smaller diameter cannulas with varied shapes and tip sizes specifically made to deliver smaller amounts of fat) to fill the desired areas with the designated portion of fat. Incisions for cannula sites average less than 5 mm. The [name] Cannula System is not experimental and is commercially available in the United States and in compliance with Federal regulations for surgical instruments. A maximum fat graft volume, to include control grafts and SVF-concentrated grafts, of 300mL will be injected. The graft volume necessary to treat the stump site will be determined by the clinical judgment of [name]. They are plastic surgeons who have significant experience in fat grafting techniques. In addition, previous high-resolution 3D CT scans will be used to help determine the fat volume needed to treat. As is standard of care for fat grafting, the fat will be injected in small 3mL syringes to prevent excessive ischemia that may otherwise be seen with larger graft volumes. If additional SVF

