5 Health-related biomedical or behavioral outcome is defined as the pre-specified goal(s) or condition(s) that reflect the effect of one or more interventions on human subjects’ biomedical or behavioral status or quality of life. Examples include: positive or negative changes to physiological or biological parameters (e.g., improvement of lung capacity, gene expression); positive or negative changes to psychological or neurodevelopmental parameters (e.g., mood management intervention for smokers; reading comprehension and /or information retention); positive or negative changes to disease processes; positive or negative changes to health-related behaviors; and, positive or negative changes to quality of life.

CS18.0 * Based on the above information, does this study meet the NIH definition of a clinical trial? Yes No

If Yes, click Save and then Click Here For Study Team's CITI Training Records . Please ensure all personnel's training is up to date

[reviewer notes-]

Section 1 - Study Objective, Specific Aims, Background and Significance

1.1 Objective: What is the overall purpose of this research study? (Limit response to 1-2 sentences.)The objective of this study is to assess the efficacy of minimally invasive autologous fat transfer at the amputation sites and the modulation of pain at the respective sites. We hypothesize that autologous fat grafting can provide a minimally invasive therapy facilitated by enabling technology of specialized instrumentation to effectively mitigate pain syndromes at amputation sites, by introducing volume stable

Section: Section 1 - Objective, Aims, Background and Significance

subcutaneous tissue over bony prominences and peripheral nerve trunks, thereby avoiding surgical revisions and preserving limb length. The premise of this study is that we will compare two minimally invasive techniques as an alternative to invasive operations, with the understanding that this therapy does not preclude more invasive procedures in the future. We further hypothesize that enriching the fat graft with autologous adipose stromal cells utilizing the Tissue Genesis Cell Isolation System (CIS), a regenerative medicine approach, will lead to improved retention of the fat graft over time and result in a more favorable outcome.

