- 1.2 Specific Aims: List the goals of the proposed study (e.g., describe the relevant hypotheses or the specific problems or issues that will be addressed by the study).1) Treat painful amputation sites in 30 patients with fat grafting to provide additional subcutaneous tissue padding over bony structures and nerve trunks. Limb anatomy and healing of the graft over time, along with stability/persistence of the new tissue, will be assessed by high resolution CT scanning with 3D reconstruction. Patients will be followed for 24 months after treatment to define long term outcomes. The primary outcome measures will be pain at the amputation site and improved ability to tolerate a prosthesis. Patients will be randomized to receive either standard fat grafting (15 patients) or cell enriched fat grafting (15 patients) utilizing the Tissue Genesis Cell Isolation System (CIS). Patients will be enrolled who have pain at an amputation site that limits function and/or interferes with the ability to use a prosthesis.2) Assess biologic properties of the cells within the fat graft and correlate with clinical outcomes. This will include adipose stem cell yield per volume of fat tissue, cell proliferation, capacity for adipogenic differentiation, lipolysis, and cell sub-population analysis by multiparameter flow cytometry. Results of these assays will be correlated with graft volume retention to search for predictors of good clinical outcome that are related to variation in adipose biology between subjects.3) Measure quality of life in patients before and after autologous fat grafting using validated psychosocial measures. This will include, among other tools, SF 36, the Beck inventory, and instruments designed for assessing limb function.

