
Section: Section 1 - Objective, Aims, Background and Significance

program, led by [name] (Co-Director of the Adipose Stem Cell Center) in collaboration with [name], director of the clinical laboratories for cell processing. We are currently starting a fully funded project with the Armed Forces of Regenerative Medicine (AFIRM). We are utilizing our extraction techniques to perform SVF enriched fat grafting for facial trauma reconstruction and this has received IRB approval at our institution. This process is regulated under human cells, tissues and cellular and tissue-based products (HCT/P) guidelines under section 361 of the CFR (21CFR1271.10). HCT/P therapies are exempt from the requirement for the submission of an Investigational New Drug (IND) application. For this project proposal, we have expanded the team to encompass expertise in reconstructive fat grafting, lower extremity reconstruction, physical medicine and rehabilitation, prosthetic design, nutritional support, and evaluation of psychosocial outcomes. Given the initial success with autologous fat grafting for facial reconstruction after trauma (analysis ongoing), even without enrichment of the graft with adipose stromal cells, we believe this therapy can be effectively applied for the treatment of limb pain. This procedure can be performed on an outpatient basis with no significant incisions on the limb, only small port sites measuring less than 5 mm. It is noted that this is a completely new, experimental application of a conventional treatment.

1.4

Significance: Why is it important that this research be conducted? What gaps in existing information or knowledge is this research intended to fill? This study will significantly impact military trauma care by validating a minimally invasive cell based technique for alleviating pain at amputation sites and improving function with a prosthesis. Importantly, the goal will be reached without invasive surgery, increased risk, and a prolonged recovery. Given the high amputation rate in the current conflicts, this work is highly relevant to the care of the wounded warrior. A major goal of this study will be to transfer the techniques and knowledge gained to physicians throughout the Department of Defense healthcare system, as well as the general US healthcare team who treats amputees from non-military trauma and illness.

Section: Section 2 - Research Design and Methods

[reviewer notes-]

Section 2 - Research and Design Methods

2.1

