Visit 2 and/or 3 PO only the subject will be evaluated by the Prosthetic /Orthotics/Occupational therapy team (limited physical exam) in conjunction with the PI to determine weight bearing readiness as well as readiness to obtain a standard of care check socket by their primary prosthetist. The participant's prosthetic device (including check socket and or permanent socket) and any other assistive devices used will be fitted as part of their routine standard of care and will only be documented that the visit happened. The subject will be instructed NOT to wear the prosthetic sockets until seen by research team and/or clearance received to utilize any new prosthetic devices which is anticipated to occur at approximately POV3 or POV4. The subject may be asked to attend an interim visit at 4-5 months PO, if the check socket and permanent socket fabrication fall out of the PO visit 2-3 range. At Post op visit 4 (6 months post op), POV5 (month 12) and POV6 (month 24) the prosthetist and therapist will implement the assessments and select the appropriate assessments based on the participant's functional status, amputation site(s), and assistive technology used. The following assessments are dependent upon the location (upper verses lower extremity) and may or may not be completed depending upon the site of interest. a. Prosthetics Evaluation Questionnaire (PEQ) is a self-report questionnaire containing 54 questions organized into nine functional domains related to prosthesis-related changes in quality of life. The PEQ was developed to fill the need for a comprehensive self-report instrument for individuals with lower limb loss. (Legro 1998). Psychometric analysis supported the reliability and validity of the PEQ for evaluating the function of the prosthesis and the major health related quality of life domains. The PEQ is estimated to take 15 minutes or less to complete. b. The 6 Minute Walk Test (6MWT) is a reliable measure of functional capacity, involves a moderate degree of exercise intensity, and is related to a moderate degree to postural control abilities in persons with lower-limb amputations. (Lin S-J, Bose NH, 2007). This 6MWT is estimated to take 20 minutes or less to complete, including the baseline rest period, set-up, and 6 minutes of continuous walking. This test will not be conducted if the participant is not able to functionally ambulate with use of prosthetic device. c. The Amputee Mobility Predictor (AMP) is a 21 item instrument designed to assess determinants of the lower-limb amputee ability to ambulate. The AMP is estimated to take approximately 15 minutes or less to complete. d. Lower Extremity Functional Scale (LEFS) is a self-reported questionnaire containing 20 questions about a person's ability to perform everyday tasks. The LEFS is anticipated to take approximately 10 minutes or less to complete. e. The Disabilities of the Arm, Shoulder, and Hand (DASH) outcome Measure is a 30-item, self-report questionnaire designed to

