Pain and Serial computed tomography imaging will be performed and measured as parametric data sets before fat grafting and afterwards at various time points using a paired t-test model. Repeated measures analysis of variance will be used to evaluate change over time in all outcome measures. Using standard conventions of alpha=0.05 and beta=0.8, an enrollment of thirty patients may provide sufficient power to detect a Cohen's effect size of about 0.9 which is anticipated to be adequate for detecting clinically meaningful differences in the volume of soft tissue. A composite functional score will be constructed from the prosthetics and occupational therapy evaluations and compared between study groups. The details of this analysis, including which evaluations will be included in the score and relative weight, can be best determined as the study progresses and initial data sets are acquired. Additionally, each assessment score from the specific tests will also be considered individually for comparison.

[reviewer notes-]

Section 2 - Research Design and Methods

2.19

Will this research be conducted in (a) a foreign country and/or (b) at a site (e.g., Navajo Nation) where the cultural background of the subject population differs substantially from that of Pittsburgh and its surrounding communities?* No

Note that copies of training records, licenses, certificates should be maintained in the study regulatory binder and are subject to audit by the Research Conduct and Compliance Office (RCCO).

Section: Section 2 - Research Design and Methods

In addition, individuals planning to conduct human subject research outside the United States must complete an optional module on the CITI training website: International Studies. Click [here](#) to access the instruction sheet for accessing optional CITI modules.

- 2.19.1 Address the following for each of the foreign/culturally different sites where this research will be conducted:
- Name of site
 - Name of authorized individual (e.g., IRB Chair) from the local IRB or other human subject protections entity that is responsible for the review and approval of the project; upload approval letter with an English translation, if applicable
 - Name and qualifications of the site collaborator responsible for the conduct of the research (e.g., site PI)
 - The anticipated number of subjects that will be enrolled at that site
 - If Federally funded, provide the Federalwide Assurance number (FWA) assigned to the site *

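### Section 1.1 sets out to show that fat grafting works, but every operated patient is grafted, so before-after change in pain and prosthesis tolerance cannot support that conclusion

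*Combined protocol and SAP*

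**What the plan says.** Section 1.1 gives the purpose as "The objective of this study is to assess the efficacy of minimally invasive autologous fat transfer at the amputation sites" and follows it with an absolute hypothesis: "We hypothesize that autologous fat grafting can provide a minimally invasive therapy". The same section then says the premise is that "we will compare two minimally invasive techniques as an alternative to invasive operations", and adds a second hypothesis that cell enrichment improves graft retention and outcome.

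Section 1.2 allocates 15 patients to standard grafting and 15 to enriched grafting. Section 2.6 names standard graft as the control treatment. Section 2.3 describes the study as non-blinded, and 2.3.1 says there is no placebo arm.

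Section 2.17 lists pain, prosthesis tolerance and stable adipose volume as primary outcomes, compared between the two arms. Section 2.18 analyses pain and imaging "before fat grafting and afterwards at various time points using a paired t-test model", and all outcomes over time by repeated-measures ANOVA.

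Section 2.7 tells patients not to wear their sockets until seen or cleared, expected at about POV3 or POV4 (month 3 or 6). At visit 2 and/or 3 the team judges "readiness to obtain a standard of care check socket by their primary prosthetist". The check and/or permanent socket, or other assistive device, is then fitted as routine care.

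Section 1.4 says the study will make its impact by "validating a minimally invasive cell based technique for alleviating pain at amputation sites". The abstract (CS2.1) repeats both this and the objective.

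**The concern.** Whether fat grafting relieves pain is a question about grafting versus not grafting, and no comparison in the trial isolates that. The randomised contrast shows only whether enrichment adds something to a graft that both arms receive. The absolute question is left to within-patient change, which mixes the graft with everything else that happens between baseline and follow-up.

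If pain falls significantly from baseline, sections 1.1 and 1.4 as worded invite the reader to take this as evidence that grafting is efficacious, and even validated. Section 1.4 looks ahead to transferring the technique through military and general healthcare. Section 3.12 says that no quantitative reports exist on pain change after grafting at amputation sites, so the plan has no external benchmark to stand in for a control.

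**Working it through.** **1. The plan's own figure.** Section 2.18 states a detectable Cohen's effect size of about 0.9 with 30 patients, alpha 0.05 and 80% power (written as beta=0.8; sidedness not given). For 15 versus 15, the detectable d is √(2/15) × (z for alpha + z for power).
- One-sided: 0.3651 × (1.645 + 0.842) = 0.908. This reproduces the figure.
- Two-sided: 0.3651 × (1.960 + 0.842) = 1.023.
- A two-sided paired t-test in all 30 patients would detect a standardised change of 0.53.

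The stated 0.9 thus fits the between-arm contrast, not the before-after test. The sample-size statement lends nothing to the absolute objective.

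**2. What can lower pain or improve tolerance without a graft effect.**
- *Rest from the socket* until about month 3 or 6 (section 2.7).
- *Refitting* of a check and/or permanent socket before the later assessments, for patients who use a prosthesis (section 2.7). Section 3.13 also admits patients limited in using an assistive device, who may receive no socket.
- *Unblinded self-report* of pain (sections 2.3, 2.5.1 and 2.7).
- *Regression to the mean*, possible because entry requires limiting pain (section 3.13).

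No analysis in section 2.18 separates these from the graft. Pain is also recorded at POV1 and POV2, before clearance is expected. Those readings avoid the new socket but fall within the no-wear period.

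**3. Illustration of size.** Take regression to the mean alone and assume no graft effect. Let patients enter m SD above the population mean, with repeat correlation r. Both values are assumptions, because the documents give neither an SD nor a correlation.
- Expected fall = m(1 − r) SD.
- SD of change = √(2(1 − r)), taking unit variance at both readings.
- Standardised change dz = m(1 − r)/√(2(1 − r)) = m√((1 − r)/2).
- Rejection probability comes from the noncentral t with 29 df and noncentrality dz√30, two-sided 5%.

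| Entry excess m | r | Fall (SD) | dz | Paired test significant |
|---|---|---|---|---|
| 0.25 | 0.7 | 0.075 | 0.097 | 8% |
| 0.25 | 0.5 | 0.125 | 0.125 | 10% |
| 0.5 | 0.7 | 0.150 | 0.194 | 18% |
| 0.5 | 0.5 | 0.250 | 0.250 | 26% |
| 1 | 0.7 | 0.300 | 0.387 | 54% |
| 1 | 0.5 | 0.500 | 0.500 | 75% |

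The nominal rate is 5%. Rest, refitting and unblinded reporting are not included in these figures.

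**4. Any non-graft cause.** If pain improves by 0.25 or 0.5 baseline SD for any reason other than the graft, dz = change/√(2(1 − r)). With r from 0.3 to 0.7, the same test rejects in 20-40% or 61-93% of trials.

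**The case against.** The strongest reply is that the trial already asks the right randomised question. Section 1.1 calls the comparison of two techniques its premise, section 2.17 compares the primary outcomes between arms, and the study is labelled a pilot. The word about validation sits in the significance rationale, not in the analysis plan. This stands, and it keeps the remedy small. It does not remove the absolute efficacy objective or the uncontrolled tests that would be read as answering it.

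A second reply concerns regression to the mean. Section 3.13 sets no pain-score threshold. It selects persistent failure: at least 3 months of fitting trials with at least 5 adjustments for socket users, and 3 months of adjustments for assistive-device users. Section 2.6 adds a second pain reading before grafting, though the plan does not say which reading is baseline. Both facts weaken regression to the mean and may put the true figure near the lower end of the table. The failed fittings also make a new socket alone a less likely explanation of improvement. They do not exclude it, because re-casting is only one of the adjustments that may count.

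Third, device information is already partly collected. Section 2.7 takes a device-use history before and after the procedure, and section 2.9 allows the patient's prosthetist to be asked about new components. This stands; what is missing is a plan to use it.

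Four stronger readings are tempting, and the documents do not support them:
- *Every patient gets a new socket.* Assistive-device users are eligible.
- *Patients enter when their pain is at its worst.* The criteria require limiting pain, not a peak.
- *The paired t-test is the only analysis of change.* Repeated-measures ANOVA is planned too, though it is equally uncontrolled.
- *All before-after results are uninterpretable.* Serial CT or MRI volume can describe how much tissue persists, and neither socket changes nor regression in pain scores readily explains it.

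**Conclusion.** The point holds for pain and prosthesis tolerance, and for function. For these outcomes the design cannot support the absolute efficacy objective in section 1.1. That conclusion follows from the allocation and the visit schedule and depends on no assumed figure.

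The size is uncertain. Under the assumptions shown, regression to the mean alone raises the chance of a significant paired test from 5% to about 8-10%, 18-26% or 54-75%, for an entry excess of 0.25, 0.5 or 1 SD above the population mean. A reader might take the top of that range as the expected error rate. Nothing in the documents supports an excess of 1 SD, and the entry rule and second pre-graft reading point lower.

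The randomised comparison of enriched with standard grafting is not undermined by this point, because the no-wear instruction and refitting apply to both arms. It remains open to the ordinary limits of a non-blinded trial with 15 patients per arm.

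**What to change.** 1. **Section 1.1, and the matching text in CS2.1:** make enriched versus standard grafting the inferential objective. Keep the absolute effect of grafting as a descriptive aim.
2. **Section 2.18:** report before-after change in pain, tolerance and function as uncontrolled estimates with confidence intervals, and make no efficacy claim from them. State which pre-graft pain reading is baseline. Imaging volume can still be reported as persistence of tissue.
3. **Sections 2.7 and 2.9:** use the device history already collected to report, by arm, the date and type of any new socket or assistive device, so that pain readings can be placed in time against refitting.
4. **Section 1.4, and the matching text in CS2.1:** replace the word about validation with wording that fits an uncontrolled pilot estimate.

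This needs no extra patients or visits and no change in care; item 3 adds a little data handling. The price is a more modest claim about fat grafting itself.
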